6.3 Duration of Follow-up

Follow-up visit procedures are listed in Section 6.1.5 and Section 6.1.7. All participants will be followed for up to 1 year after the last dose of pembrolizumab and vactosertib is administered or 2 years after surgery, whichever occurs last. Follow-up assessments will occur according to Section 6.1.5, if discontinuation occurs post-surgery, or according to Section 6.1.7 if discontinuation occurs during and/or after post-adjuvant treatment. Follow-up assessments will occur until PD, death, withdrawing consent or becoming lost to follow-up, whichever occurs first.

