- Participants who meet study eligibility criteria (Section 3.3) and have adequately recovered from toxicity or complications of a surgery or other procedure, per the assessment of the treating investigator will be offered participation in the adjuvant treatment cohort (pembrolizumab plus vactosertib). Patients who still have their primary tumor in place (i.e. not surgically removed) would not be eligible for the optional adjuvant treatment.
- If the participant meets all other eligibility criteria to receive pembrolizumab plus vactosertib (e.g., no safety issues), then they will receive adjuvant treatment 6 weeks (± 2 weeks) after hepatic metastasectomy. Participants will receive adjuvant pembrolizumab plus vactosertib for up to eight 6-week cycles (approximately 1 year) or until disease progression is radiographically documented, unacceptable adverse event(s), intercurrent illness that prevents further administration of treatment, investigator's decision to discontinue the patient, administrative reasons requiring cessation of treatment, or withdrawal of consent, whichever occurs first.
- Correlative labs will be performed every 12 weeks during the adjuvant treatment period.
- Participants will be followed for up to 1 year after the last dose of pembrolizumab is administered, or until disease progression, the start of new anticancer treatment, or withdrawal of consent, whichever occurs first.

List of Abbreviations

5-FU	5-fuorouracil
AE	adverse event
ALP	alkaline phosphatase
ALT	alanine aminotransferase
ANC	Absolute neutrophil count
AST	aspartate aminotransferase
BID	twice a day (bis in die)
CBC	complete blood cell (count)
CD	Cluster of differentiation
CEA	Carcinoembryonic antigen
CNB	core needle biopsy
CR	complete response
CRC	Colorectal cancer
CrCl	creatinine clearance
CRF	case report form
CT	computerized tomography
CTCEA	Common Terminology Criteria for Adverse Events
CTLA-4	cytotoxic T-lymphocyte-associated protein 4
CTMS	Clinical Trial Management System
dMMR	Mismatch repair deficient
DSMC	Data and Safety Monitoring Committee
DSMP	Data and Safety Monitoring Plan
ECI	events of clinical interest
ECOG	Eastern Cooperative Oncology Group
EGFR	Epidermal growth factor receptor
ELISA	enzyme-linked immunoassay
EORTC	European Organisation for Research and Treatment of Cancer
EPO	Erythropoietin
ERC	Ethics Review Committee
FDA	United States Food and Drug Administration
FFPE	Formalin-fixed paraffin-embedded

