2.3 Secondary Objectives and Endpoints

Secondary Objectives	Endpoints	Time Frame
1. To establish the safety/toxicity profile of pembrolizumab-based treatment in the perioperative setting for patients with CRC with resectable hepatic metastases.	
 Proportion of participants with Adverse Events, as graded by NCI CTCAE version 5.0 Proportion of participants with events of clinical interest (ECIs) Rates of perioperative complications 	From initiation of study treatment until 1 year post last dose of pembrolizumab.
2. To explore the efficacy of pembrolizumab plus vactosertib in patients with CRC with resectable hepatic metastases.	
 R0 resection rate Pathologic response in resected tumor Objective response rate 2-year relapse-free survival (RFS) 	From baseline to surgery. From surgery to up to 2 years post-surgery.

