3.5 Duration of Follow Up

Due to the potential for late toxicities from pembrolizumab, patients will be followed for at least 1 year after their last dose of pembrolizumab or up to 2 years post-surgery for RFS whichever occurs last.

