6.1.7 Follow-up Phase

All participants will be followed for up to 1 year after the last dose of pembrolizumab and vactosertib is administered or up to 2 years after surgery, whichever occurs last. Follow-up may end sooner if disease progression, withdrawal of consent, or death occur.

Additional post-operative chemotherapy, subsequent anti-neoplastic therapy, and follow-up assessments will be at the discretion of the treating physician. Information regarding post-study anti-neoplastic treatment will be collected if such treatment is initiated.

The following study procedures and assessments will be done Q90D (± 14 days) for up to one year after last dose of pembrolizumab and vactosertib or up to two years after surgery, whichever occurred last:

- Disease status assessment/measurable disease
- Concomitant medications
- Post-study anticancer therapy status
- Survival Status

Phase 2, Pembrolizumab, Vactosertib

- Evaluation of AEs for the timeframe defined in Section 7.5
- Radiologic CT imaging with IV contrast to monitor disease status.
- Correlative studies blood collection

Note: Safety labs and correlative labs will be collected up to 1 year post-pembrolizumab.

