6.4 Withdrawal Criteria

Discontinuation of study intervention does not represent withdrawal from the study.

As certain data on clinical events beyond study intervention discontinuation may be important to the study, they must be collected through the participant's last scheduled follow-up, even if the participant has discontinued study intervention. Therefore, all participants who discontinue study intervention before completion of the protocol-specified treatment period will still continue to be monitored in this study and participate in the study visits and procedures as specified in Section 6.1.5, if discontinuation occurs during post-surgery, and as specified in Section 6.1.6.3 and Section 6.1.6.4, if discontinuation occurs during and/or after post-adjuvant treatment.

Participants may discontinue study intervention at any time for any reason or be discontinued from the study intervention at the discretion of the investigator should any untoward effect occur. In addition, a participant may be discontinued from study intervention by the investigator or the Sponsor if study intervention is inappropriate, the study plan is violated, or for administrative and/or other safety reasons.

A participant must be discontinued from study intervention, but continue to be monitored in the study for any of the following reasons, but are not limited to, disease progression, the occurrence of an adverse event or a concurrent illness, a patient's request to end participation, or a patient's non-compliance.

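### Section 6.3 ends scheduled follow-up at progression, against the 1-year late-toxicity follow-up in 2.3 and 3.5; Section 7.5 also stops routine AE collection short of that year for every patient

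*Combined protocol and SAP*

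**What the plan says.** Section 3.5 gives the purpose and the minimum: "Due to the potential for late toxicities from pembrolizumab, patients will be followed for at least 1 year after their last dose of pembrolizumab". For RFS, the period extends to the 2-year point after surgery if that is later. Section 2.3 sets the safety time frame as "From initiation of study treatment until 1 year post last dose of pembrolizumab".

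Three places deal with progression during follow-up, and they differ in strength:

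- Section 6.3 is firm: "Follow-up assessments will occur until PD, death, withdrawing consent or becoming lost to follow-up, whichever occurs first".
- The Optional Adjuvant Treatment outline after the study schema is also firm. It follows patients for up to 1 year after the last pembrolizumab dose, "or until disease progression, the start of new anticancer treatment, or withdrawal of consent, whichever occurs first".
- Section 6.1.7 is permissive: "Follow-up may end sooner if disease progression, withdrawal of consent, or death occur".

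Section 6.4 points the other way. It says "A participant must be discontinued from study intervention, but continue to be monitored in the study for any of the following reasons", and disease progression is the first reason listed.

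Section 6.1.7 schedules disease status, imaging, survival status, later anticancer therapy and correlative blood every 90 days, with safety labs to 1 year after pembrolizumab. It limits AE evaluation to the Section 7.5 windows: 30 days after treatment for all AEs, and 90 days for SAEs (30 days if new anticancer therapy starts). Drug-related SAEs are reportable at any time.

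**The concern.** A stopping point that suits RFS is applied to the whole follow-up phase, including the part that exists for late toxicity. A site with a relapsed patient cannot comply with 6.3 and 3.5 together.

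Section 5.3.1 says immune-related events can appear several months after the last dose. The 90-day visits and labs (chemistry, hematology, thyroid function) are the plan's active means of finding them. If those stop at progression, capture becomes passive, because 7.5 does not oblige investigators to look for events in former participants. Observation time for late, mainly laboratory-detected toxicity would then depend on outcome. The effect is sharpest in adjuvant patients who relapse on treatment: treatment stops at radiographic recurrence, so under 6.3 nearly the whole post-dose year goes unobserved.

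**Working it through.** **Side-by-side reading, for a patient who progresses within the year after the last pembrolizumab dose**

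- Section 3.5: follow-up continues to at least 1 year.
- Section 2.3: the safety endpoint runs to 1 year.
- Section 6.4: monitoring continues. For adjuvant discontinuations, however, it cites only 6.1.6.3 (End of Treatment) and 6.1.6.4 (the 30-day safety visit), whereas 6.3 sends the same patients to 6.1.7.
- Section 6.3 and the adjuvant outline: follow-up ends at progression.
- Section 6.1.7: follow-up may end.
- Footnotes to Tables 10 and 11: progression limits the collection of disease-status information, while safety labs run to 1 year after pembrolizumab with no such limit.
- Section 7.5: progression ends none of the AE or SAE windows, but those windows close at 30 and 90 days.

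There are therefore two separate gaps. The first is the loss of 90-day visits and labs after progression. The second is the shortfall of 7.5 against 2.3, which affects every patient.

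**Size of the first gap**

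The documents give no figure for the share of patients affected, so there is none to reproduce. Inputs from Section 1.1 are the 3-year PFS values with perioperative FOLFOX: 42.4% in resected patients and 35.4% in randomized patients. The assumption is a constant hazard, with the 3 years counted from surgery.

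Hazard: λ = −ln(S₃)/3.

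- 42.4%: λ = 0.858/3 = 0.286 per year
- 35.4%: λ = 1.038/3 = 0.346 per year

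Event within 12 months of surgery, 1 − exp(−λ):

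- 42.4%: 24.9%, and 17 × 0.249 = 4.2 patients
- 35.4%: 29.3%, and 17 × 0.293 = 5.0 patients

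Sensitivity to hazard shape, with Weibull S(t) = S₃^((t/36)^k), t in months:

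- k = 1.5, S₃ = 42.4%: 1 − 0.424^((12/36)^1.5) = 15.2%
- k = 0.7, S₃ = 35.4%: 1 − 0.354^((12/36)^0.7) = 38.2%

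Sensitivity to time origin: if the quoted PFS applies at 32 months after surgery instead of 36, the 12-month figures become 27.5% and 32.3%.

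**Adjuvant patients**

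The eighth cycle starts at week 6 + 7 × 6 = 48 after surgery, so 1 year after the last dose is week 100.

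- Relapse on treatment: the risk between weeks 6 and 48, for a patient event-free at week 6, is 1 − exp(−λ × 42/52), or 21% (42.4%) to 24% (35.4%). These patients lose almost all of the post-dose year under 6.3.
- Completing 8 cycles: such a patient is progression-free at about week 48. The conditional risk over the next 52 weeks is 1 − exp(−0.286) = 25% (29% using 35.4%).
- Unconditional risk from surgery to week 100: 1 − exp(−λ × 100/52), or 42% (42.4%) to 49% (35.4%). This does not describe patients who complete treatment.

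**The case against.** The strongest reply is that progression is not what mainly limits late AE data. Section 7.5 closes routine AE collection at 30 days and SAE collection at 90 days for all patients, and progression shortens neither. Drug-related SAEs remain reportable indefinitely, the 30-day visit is mandatory after adjuvant treatment, and 7.7 follows AEs above Grade 1 until they resolve or new therapy starts. All of this stands. A reader might infer that late safety data as a whole are cut off at progression, or that reported AE proportions are biased downward mainly for that reason. The documents do not support either inference. It also follows that rewording 6.3 alone would not deliver the 1-year endpoint.

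The separation of disease-status from safety follow-up is also partly present already, in the footnotes to Tables 10 and 11, and 6.1.7 only permits an early end. So it is not certain that safety labs stop at progression; that is the literal reading of 6.3. This narrows the point but does not remove the conflict, because 6.3 is the section that defines follow-up duration.

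Section 6.4 does not settle the matter. It requires continued monitoring, but for adjuvant patients it names only visits up to 30 days.

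Lastly, overall survival is not an endpoint and the safety analysis is descriptive, so deaths missed after progression are a secondary matter.

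**Conclusion.** The point holds in limited form. Section 6.3 and the adjuvant outline contradict 3.5, 2.3 and 6.4 on whether follow-up continues after progression. As written, 6.3 shortens active detection of late toxicity selectively in patients who relapse. A second, independent gap is that the 7.5 windows do not reach the 1-year safety time frame for anyone.

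Under a constant hazard the first gap could touch about 25% to 29% of patients within 12 months of surgery, roughly 4 to 5 of 17, with 15% to 38% across Weibull shapes 0.7 to 1.5. These are model-based upper estimates: PFS counts deaths, which end follow-up under any rule, and the inputs come from a cited trial with a different time origin.

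Two stronger readings should be set aside. A quarter of patients is not a floor, since the lower constant-hazard value is 24.9% and a rising hazard gives less. The 42% by week 100 is not the risk for patients who complete 8 cycles; for them it is about 25% over the following year, using the 42.4% input.

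**What to change.** Reconcile 2.3, 3.5, 6.1.7, 6.3, 6.4, 7.5 and the adjuvant outline:

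1. State that progression ends only the RFS and disease-status assessments. Safety labs, AE evaluation and survival status continue to the 3.5 time point, 1 year after the last pembrolizumab dose, regardless of progression.
2. Say whether new anticancer treatment ends safety follow-up. The adjuvant outline says that it does; 3.5 and 6.3 do not.
3. Make 6.3 and 6.4 cite the same visits for patients who discontinue.
4. Align the 7.5 collection window with the 2.3 time frame, or restate 2.3 to match 7.5.
5. Report AE proportions together with the follow-up time available.

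The cost is an amendment to wording and a few extra safety contacts in progressed patients, which 3.5 already requires. Extending the 7.5 window would also add AE collection for all patients; restating 2.3 would avoid that. Late events after progression may be confounded by later therapy, but 6.1.7 already records that therapy, so they can be shown with it.

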6.4 Withdrawal Criteria

Discontinuation of study intervention does not represent withdrawal from the study.

As certain data on clinical events beyond study intervention discontinuation may be important to the study, they must be collected through the participant's last scheduled follow-up, even if the participant has discontinued study intervention. Therefore, all participants who discontinue study intervention before completion of the protocol-specified treatment period will still continue to be monitored in this study and participate in the study visits and procedures as specified in Section 6.1.5, if discontinuation occurs during post-surgery, and as specified in Section 6.1.6.3 and Section 6.1.6.4, if discontinuation occurs during and/or after post-adjuvant treatment.

Participants may discontinue study intervention at any time for any reason or be discontinued from the study intervention at the discretion of the investigator should any untoward effect occur. In addition, a participant may be discontinued from study intervention by the investigator or the Sponsor if study intervention is inappropriate, the study plan is violated, or for administrative and/or other safety reasons.

A participant must be discontinued from study intervention, but continue to be monitored in the study for any of the following reasons, but are not limited to, disease progression, the occurrence of an adverse event or a concurrent illness, a patient's request to end participation, or a patient's non-compliance.

6.4.1 Withdrawal from the Study

A patient must be withdrawn from the study if the patient or patient's legally acceptable representative withdraws consent from the study.

If a patient withdraws from the study, they will no longer receive study treatment or be followed at scheduled protocol visits.

Specific details regarding procedures to be performed at the time of withdrawal from the study are outlined in Section 6.2 (post-surgery visit). The procedures to be performed should a participant repeatedly fail to return for scheduled visits and/or if the study site is unable to contact the participant are outlined in Section 6.3.2.

6.4.2 Lost to Follow-up

If a patient fails to return to the clinic for a required study visit and/or if the site is unable to contact the patient, the following procedures are to be performed:

- The site must attempt to contact the patient and reschedule the missed visit. If the patient is contacted, the patient should be counseled on the importance of maintaining the protocol-specified visit schedule.
- The investigator or designee must make every effort to regain contact with the patient at each missed visit (e.g., phone calls and/or a certified letter to the patient's last known mailing address or locally equivalent methods). These contact attempts should be documented in the patient's medical record.
- Note: A patient is not considered lost to follow-up until the last scheduled visit for the individual patient. The amount of missing data for the patient will be managed via the pre-specified data handling and analysis guidelines.

6.5 Usage of Concurrent/Concomitant Medications/Vaccinations

Medications or vaccinations specifically prohibited in the exclusion criteria are not allowed during the treatment period. If there is a clinical indication for any medication or vaccination specifically prohibited, discontinuation from trial therapy may be required. The investigator should discuss prohibited medications/vaccinations with the Merck Clinical Director. The final decision on any supportive therapy or vaccination rests with the investigator and/or the patient's primary physician. However, the decision to continue the patient on study treatment requires the mutual agreement of the investigator, Merck, and the patient.

6.5.1 Acceptable Concomitant Medications

All treatments that the investigator considers necessary for a patient's welfare may be administered at the discretion of the investigator in keeping with the community standards of medical care. All concomitant medication will be recorded on the case report form (CRF) including all prescription, over-the-counter (OTC), herbal supplements, and IV medications and fluids. If changes occur during the trial period, documentation of drug dosage, frequency, route, and date may also be included on the CRF.

All concomitant medications received within 28 days before the first dose of trial treatment and 30 days after the last dose of trial treatment should be recorded. Concomitant medications administered after 90 days after the last dose of trial treatment should be recorded for SAEs and ECIs as defined in Section 7.5.

6.5.2 Prohibited Medications

If during the course of the trial, a patient requires treatment with following medicines for a limited period of time, it should not be given concurrently with the study treatment and its use should be reviewed with the Sponsor-Investigator who will provide guidance based on the half-life of the medication as well as other clinical considerations. The Investigator is also advised to consider

alternative medicines. Listed below are specific restrictions for concomitant therapy or vaccination during the study:

- Antineoplastic systemic chemotherapy or biological therapy not specified in this protocol
- Immunotherapy not specified in this protocol
- Chemotherapy not specified in this protocol
- Investigational agents other than pembrolizumab and vactosertib
- Radiation therapy
 - Note: Radiation therapy to a symptomatic solitary lesion or to the brain may be allowed at the investigator's discretion.
- Live or live attenuated vaccines within 30 days prior to the first dose of triaQI treatment and while participating in the trial. Note: killed vaccines are allowed.
- Systemic glucocorticoids for any purpose other than to modulate symptoms from an event of clinical interest of suspected immunologic etiology. The use of physiologic doses of corticosteroids may be approved after consultation with Merck.
- Liver directed therapy such as radiotherapy or yttrium-90
- Rifaximin or lactulose to control encephalopathy
- Strong CYP3A inhibitors including but not limited to clarithromycin, itraconazole, ketoconazole, nefazodone, neflifinavir, saquinavir, voriconazole - *Grapefruit juice is not allowed in the study. The topical use of medications, such as 2% ketoconazole cream, may be allowed when discussed with the Sponsor-Investigator.*
- Potent CYP3A inducers, including but not limited to carbamazepine, phenytoin, rifampin - *St. John's Wort is not allowed*
- Drugs that prolong QT Interval and have a risk of Torsades de Pointes

Patients who, in the assessment by the investigator, require the use of any of the aforementioned treatments for clinical management should be removed from the trial.

All concomitant medications received within 28 days prior to the first dose of study treatment and up to 30 days after the last dose of study treatment should be recorded. Concomitant medications administered 90 days after the last dose of study treatment should be recorded for SAEs and ECIs as defined in Section 7.5.

There are no prohibited therapies during the Post-Treatment Follow-up Phase.

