8.3 Interim Analyses and Stopping Rules

The trial will be stopped early if 2 of the first 6 patients fail to undergo liver resection surgery within 6 weeks of their final chemotherapy treatment (if applicable) due to AEs attributed to pembrolizumab-based treatment, or experience Grade IV-V surgical complications according to Clavien-Dindo classification attributed to pembrolizumab -base treatment (Appendix 4).

Of particular significance to this study, enrolling patients being treated with curative intent, are perioperative complications attributed to pembrolizumab-based treatment. These may include delaying surgery due to pre-operative AEs and complications during or after surgery attributed to pembrolizumab-based treatment. Early stopping rules have been defined to mitigate risk of perioperative complications. The study will be stopped and the approach will be re-evaluated if 2 or more of the first 6 patients experience any one of the following:

- A delay in planned surgery beyond the 6-week window from final chemotherapy (if applicable), due to any grade toxicity attributable to study treatment. Delays in surgery due to other reasons (scheduling, available O.R time, patient preference) will not count.
- Grade IV and V surgical complications according to Clavien-Dindo classification (Appendix 4). *Note:* Surgical complications associated with liver metastectomy are very common, and we recognize that it may be difficult to attribute any such complications to preoperative administration of pembrolizumab. Therefore, the occurrence of such events may not necessarily require stopping the study early, but will be discussed amongst members of the JSC, with particular attention paid to specific complications such as liver failure, severe colitis, etc.

Enrollment will be paused for 4 weeks after the sixth patient undergoes surgery (or receives their last dose of pembrolizumab if unable to undergo surgery). During this interval the study investigators will meet with the participating surgeons to review the first 6 cases. A recommendation will be made regarding whether or not to enroll additional patients and if any changes are needed to optimize safety or feasibility.

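### Section 6.5.2 takes patients who need a listed treatment off the trial, while Sections 6.4 and 6.5 stop only study treatment; read literally, it may end scheduled follow-up for reasons related to outcome

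*Combined protocol and SAP*

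**What the plan says.** All references are to the combined protocol and SAP.

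- **Section 6.5.2, opening:** if a patient "requires treatment with following medicines for a limited period of time, it should not be given concurrently with the study treatment", and the use is reviewed with the Sponsor-Investigator. Several listed items carry their own exceptions, for example "Radiation therapy to a symptomatic solitary lesion or to the brain may be allowed at the investigator's discretion".
- **Section 6.5.2, close:** patients who, in the investigator's assessment, "require the use of any of the aforementioned treatments for clinical management should be removed from the trial". The list includes systemic glucocorticoids other than for immune-type events of clinical interest (ECIs), and "Rifaximin or lactulose to control encephalopathy". The section then lifts all prohibitions for the post-treatment follow-up phase.
- **Section 6.5 (parent section):** where a prohibited medicine is clinically indicated, "discontinuation from trial therapy may be required". It does not mention leaving the trial.
- **Section 6.4:** "Discontinuation of study intervention does not represent withdrawal from the study". Patients whose study treatment is stopped, including for an adverse event (AE) or a concurrent illness, remain under study monitoring.
- **Section 6.4.1:** the one stated ground for mandatory withdrawal is withdrawn consent. After withdrawal, "they will no longer receive study treatment or be followed at scheduled protocol visits".

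**The concern.** A site facing a patient who needs a listed medicine finds two instructions. One ends study treatment, and the other appears to end participation. If the second is followed, scheduled visits stop.

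The need for several listed items is plausibly related to how the patient is doing. Non-immune glucocorticoid use may accompany a complication. Treatment for encephalopathy may accompany the kind of event that Section 8.3 wants discussed "with particular attention paid to specific complications such as liver failure, severe colitis, etc". Missing data that arise this way are informative, and in a trial of 17 to 19 patients a few cases matter. At stake are safety information in the later part of the planned period and RFS status in patients not yet known to have progressed.

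**Working it through.** No planned figure is in dispute, so there is none to reproduce. The check sets the sections side by side and then gives a scale.

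**1. Do the rules meet on the same patient?** Yes. An AE or concurrent illness that creates the need for a listed medicine is also among the Section 6.4 reasons for stopping study treatment while monitoring continues. Sections 6.4 and 6.5.2 then give that patient different outcomes.

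**2. When does the removal sentence apply?** Section 6.5.2 exempts only post-treatment follow-up. The neoadjuvant cycle and the adjuvant phase (up to 8 × 6 = 48 weeks) are not exempt. The perioperative interval is unclear, because Table 10 lists Surgery and Post-Surgery Safety Follow-up in columns separate from the Follow Up Phase.

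**3. What safety information survives removal?** Section 7.5 requires AE reports for 30 days after treatment stops. It requires SAE reports for 90 days, or 30 days if new anticancer therapy starts. Section 7.6 has a 90-day window for the vactosertib supplier. Section 7.7 continues follow-up for patients removed because of unacceptable AEs, but does not mention removal for a prohibited medicine.

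The Section 2.3 safety endpoint runs to 1 year after the last pembrolizumab dose. If both clocks start on the same day (an assumption), the part beyond the windows is 365 − 30 = 335 days for AEs and 365 − 90 = 275 days for SAEs. Section 6.1.7 itself ties AE evaluation to the Section 7.5 windows. What scheduled visits add later is therefore mainly the safety laboratory tests to 1 year and the chance to learn of late drug-related SAEs, which remain reportable. Section 7.5 does not oblige investigators to seek events in former participants.

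**4. What happens to RFS?** Section 7.1 defines 2-year RFS as the proportion without radiographic progression within 2 years of resection. Section 8.4.1 evaluates it in resected patients. Section 8.4 gives no censoring or missing-status rule. A resected patient removed before documented progression has unknown 2-year status. Counting that patient as progression-free can only raise the reported rate or leave it unchanged.

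**5. Scale.** If k of n patients have unknown status, the gap between the best-case and worst-case proportion is k/n. The documents give no removal rate, so k is assumed. The values of n are the 17 evaluable and 19 enrolled patients in Section 8.2.2.

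| k (assumed) | n = 17 | n = 19 |
|---|---|---|
| 1 | 1/17 = 5.9 points | 1/19 = 5.3 points |
| 2 | 2/17 = 11.8 points | 2/19 = 10.5 points |
| 3 | 3/17 = 17.6 points | 3/19 = 15.8 points |
| 4 | 4/17 = 23.5 points | 4/19 = 21.1 points |

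The number of resected patients is not fixed in advance. If it is below 17, each patient weighs more.

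**The case against.** The strongest reply is that removal under Section 6.5.2 need not mean withdrawal under Section 6.4.1. The sentence ending visits in Section 6.4.1 concerns patients who withdraw, and it does not refer to Section 6.5.2. Section 6.4 says plainly that patients whose treatment stops are still monitored. A careful site could read the sections together and lose nothing. This stands in part: loss of data is a risk under the literal reading, not a consequence that the protocol states.

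A reader might also infer stronger things that the documents do not support:

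- **That relapses would go missing.** Radiographic progression is itself the RFS event, and Sections 6.1.7 and 6.3 end follow-up at progression in any case. Adjuvant imaging is every 12 weeks and again at end of treatment. No therapy is prohibited in post-treatment follow-up. RFS is exposed only when a listed treatment is needed before progression is documented.
- **That safety data in general are lost, or that removed patients leave the safety denominator.** The 30- and 90-day reporting duties continue. Section 8.4.1 bases safety analyses on everyone who received at least one dose.
- **That every patient needing a listed medicine is affected.** The limited-use provision and the item exceptions narrow the group.
- **That primary-endpoint specimens would be lost.** Nothing says that needing a listed medicine cancels surgery. Section 6.1.4 provides for surgery when vactosertib is held and for a second biopsy if surgery is cancelled. Section 8.2.2 allows replacement.

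These limits narrow the point but do not remove it. The Section 7.7 protection is confined to removal for unacceptable AEs, the reporting windows are shorter than the endpoint's time frame, and nothing in Section 6.5.2 tells the site that follow-up continues.

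**Conclusion.** The contradiction is established from the text: Section 6.5.2 disagrees with its own opening, with Section 6.5 and with Sections 6.4 and 6.4.1. The statistical consequence is conditional. If a site treats removal as the end of participation, later safety information and RFS status before documented progression may be missing in patients selected by their clinical course. Each such patient is worth 5.3 to 5.9 percentage points at the planned size. How many there would be is unknown, and any total is an assumption. The conclusion also assumes that need for the listed medicines is related to outcome. That is plausible for glucocorticoids and encephalopathy treatment, but the documents do not quantify it. The point deserves correction and does not undermine the design.

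**What to change.** Reconcile Section 6.5.2 with Sections 6.4 and 6.5 so that it is clear whether study treatment or study participation ends when a listed treatment is needed. Which rule governs study treatment is for the sponsor to decide, and no view on it is offered here.

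Then add to Section 6.5.2 that, whatever is decided about study treatment, the patient stays in the study for planned specimen collection and for safety, disease-status and survival follow-up unless consent is withdrawn. The prohibited medicine and its start date should be recorded.

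The cost is a short wording change in an amendment, and the visits are already scheduled. The drawback is that some follow-up data will come from patients taking other medicines. The recorded start date lets the analyst show which data those are.
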